## **11.5. Pregnancy Tests**

Pregnancy test results will be provided in a listing.

## **11.6. Vital Signs**

Routine vital signs, including blood pressure, respiratory rate, temperature, and heart rate will be measured at Screening, Week -6, Week -4, Day 1 and Weeks 2, 4, 6, 8, 10, 12, 14, 16, 18, 20, 22, 24, 26, 28, 30, 32, 34, 36, 38, 40, 42, 44, 46, 48, 50 and the End of Pegloticase Infusions Visit (if applicable), Week 52/End of Study/Early Termination and 3 and 6 month Post Treatment Follow-up Visits. During the Pegloticase + IMM Period study visits, vitals should be taken before the pegloticase infusion and any time after the end of the infusion, but prior to subject's discharge/release from the site.

At sites who participate and from subjects who consent, optional intensive blood pressure measurements will be taken prior to the infusion on Day 1 and at Weeks 6, 12, 18, 24, 30, 36, 42, 48 and at the non-infusion End of Pegloticase Infusions Visit (if applicable) and Week 52/End of Study/Early Termination Visit. At these intensive blood pressure collections, three blood pressure measurements should be performed, at least 2 minutes apart, with blood pressure readings measured to the nearest mmHg prior to pegloticase infusion. If any of the 3 systolic blood pressure measurements differ by more than 8 mmHg or if diastolic measurements differ by more than 5 mmHg, a repeat sets of 3 sitting blood pressure measurements will be obtained until the difference is less than 8 mmHg for systolic and less than 5 mmHg for diastolic. All values will be recorded in the eCRF. Additional sets of 3 measurement may be taken until none of the 3 systolic measurements differ by 8 mmHg and none of the 3 diastolic measurements differ by more than 5 mmHg. The average of the 3 values will be used in the summary. If more than 1 set of measurements is taken, the set of measurements performed last will be used for the pre-infusion timepoint at a visit.

Weight should be measured in kilograms or pounds without shoes and recorded at the Screening Visit and prior to dosing MTX Week -6 Visit; prior to pegloticase infusion on Day 1 and at the Weeks 8, 16, 24, 36 and at the non-infusion End of Pegloticase Infusions Visit (if applicable), Week 52/End of Study/Early Termination and Months 3 and 6 Post Treatment Follow-up Visits.

Height will be collected at the Screening Visit only. BMI will be determined using the weight recorded in kg and the height measured at screening.

Descriptive summaries of observed and change from baseline values will be presented for each vital sign parameter by pegloticase treatment status (On Treatment, Post-Treatment, and Overall, see Section 9.4), and visit, using the safety population. Vital sign measurements that are monitored as a result of an infusion-associated event will not be included in the descriptive summaries but will be presented in subject listings.

The following conversion factor will be used to convert any temperatures reported in degrees Fahrenheit to Celsius:

Temperature (in °C) = 5/9 (Temperature [in °F]-32).

The following conversion factor will be used to convert any weights reported in pounds to kilograms:

This document is confidential.

Weight [kg] = Weight [in lbs] \* 0.4536.

The following formula will be used to determine the BMI (in kg/m^2) using weight [in kg] and height [in cm]:

BMI = Weight / (Height/100);

### **11.7.      Electrocardiograms**

A 12-lead ECG will be performed at Screening and at the discretion of the Investigator thereafter. The results will be recorded as normal or abnormal on the eCRF and all abnormal results will be evaluated as clinically significant (CS) or not clinically significant (NCS) by the investigator.

Using the safety population, a summary will be provided of subjects at Screening (using the count and percentage of subjects) with:

- Normal
- Abnormal NCS
- Abnormal CS

Percentages will be based on the number of subjects with an assessment completed.

Because the post-Screening ECGs are done at the discretion of the investigators, or in the event of an infusion reaction, only the following summaries will be provided using the safety population:

- Incidence of post-Screening Abnormal ECGs (includes NCS and CS) findings
- Incidence of post-Screening Abnormal, Clinically Significant ECGs

For the post-Screening ECG summary, percentages will be calculated using the number of subjects who have a post-Screening assessment.

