## 7.2 Rationale for this Study

Immunogenicity (anti-pegloticase antibodies) in response to pegloticase therapy may lead to loss of therapeutic response and/or AEs, including IRs. In the phase 3 studies, IRs occurred more commonly in subjects whose sUA values increased above 6 mg/dL, after initially showing response following the first 1 or 2 infusions. The titer of the anti-drug antibody was also associated with loss of response, with subjects having the highest levels of anti-drug antibodies showing the lowest response rates.

The development of anti-drug antibodies can be influenced by drug and treatment-related factors, as well as patient characteristics. A potential prophylactic strategy to manage anti-drug antibody response with pegloticase is the co-administration of immunomodulatory therapy. Various methods are used to reduce antibody production in other settings, the most common of which is the use of traditional rheumatoid arthritis disease-modifying drugs, such as MTX, azathioprine,

mycophenolate mofetil, leflunamide, and others, as is commonly implemented with rheumatoid arthritis biological therapy (e.g., infliximab and other infusible and subcutaneous antibody products) [Strand et al, 2017].

MTX is the most commonly used non-biological disease modifying agent worldwide and is frequently used in combination with other biological therapies [Strand et al, 2017].

In the current study, MTX will be evaluated for its ability to improve the response rate and reduce IRs with pegloticase by reducing drug immunogenicity. Prospective use of sUA stopping rules, with pegloticase treatment cessation (but study continuation) when a subject has an sUA level > 6 mg/dL on two consecutive study visits, will also help confirm the value of this approach to reduce IR risk.

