#### **9.5.4.6 Electrocardiogram**

A 12-lead ECG will be performed at Screening and at the discretion of the Investigator thereafter.

When possible, a 12-lead ECG will also be performed at the time the AESI (See Section [9.5.4.1.1.5](#)) of infusion reaction, anaphylaxis and cardiovascular events is suspected.

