#### 11.3.1. Adverse Events of Special Interest

Adverse events of special interest (AESI) will include: IRs, anaphylaxis, gout flares, and cardiovascular events. All adverse events of special interest will be summarized using MTX population for MTX Tolerability Period and Safety population for Run-in and Pegloticase + IMM Period, adjudicated as well as any identified by programming. IRs and anaphylaxis will be summarized in Pegloticase + IMM Period only. An independent external adjudication committee will review reported events of infusion reactions, cardiovascular events and anaphylaxis. The AESI of gout flare will not be adjudicated.

When possible, a 12-lead ECG will be performed at the time the AESI of infusion reaction, anaphylaxis and cardiovascular event is suspected

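### SAP 11.7 labels as incidence the abnormal fraction among subjects who happened to have a post-Screening ECG, and as written it counts abnormalities unchanged since Screening (minor)

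*SAP*

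**What the plan says.** **When ECGs are taken.** Protocol 9.5.4.6: "A 12-lead ECG will be performed at Screening and at the discretion of the Investigator thereafter". SAP 11.3.1 adds event-prompted recordings: "When possible, a 12-lead ECG will be performed at the time the AESI of infusion reaction, anaphylaxis and cardiovascular event is suspected". The protocol has the same prompt in 9.5.4.6 and in footnote 9 to the Schedule of Assessments.

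**What is summarised.** SAP 11.7 acknowledges the irregular collection ("Because the post-Screening ECGs are done at the discretion of the investigators, or in the event of an infusion reaction") and for that reason limits the post-Screening output, in the safety population, to two items:

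- "Incidence of post-Screening Abnormal ECGs (includes NCS and CS) findings"
- "Incidence of post-Screening Abnormal, Clinically Significant ECGs"

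**Denominator.** "For the post-Screening ECG summary, percentages will be calculated using the number of subjects who have a post-Screening assessment".

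**Screening.** The Screening ECG is summarised separately on a three-level scale: normal, abnormal not clinically significant (NCS), abnormal clinically significant (CS). Later abnormal readings are graded NCS or CS in the same way. No shift from Screening is planned, and neither item is restricted to new or worsened findings.

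**Expected treatment effect on a trigger.** Protocol 7.2: "MTX will be evaluated for its ability to improve the response rate and reduce IRs with pegloticase by reducing drug immunogenicity".

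**The concern.** An incidence needs a numerator of new events and a denominator of subjects at risk. SAP 11.7 has neither.

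The denominator is the set of subjects who had a post-Screening ECG. Entry to that set happens after randomisation and depends partly on events that the trial compares between arms. If MTX lowers the infusion-reaction rate, fewer MTX subjects are likely to have an ECG, and those who do may not resemble the placebo subjects who do. The percentage then mixes the frequency of abnormal findings with the frequency of recording.

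The numerator is any abnormal post-Screening reading. Read literally, a subject whose NCS abnormality at Screening is unchanged at a later ECG counts as incident.

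The SAP is stricter elsewhere. Section 11.6 keeps vital signs monitored because of an infusion-associated event out of the descriptive summaries. Section 11.4 gives laboratory tests shift tables from baseline. For ECGs, event-prompted readings make up much of the summary, and the Screening reading is not used as a reference.

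What is at stake is how a side-by-side safety table is read, in a trial where infusion reactions and cardiovascular events are of special interest.

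**Working it through.** The documents give no expected figure for the ECG table, so there is none to reproduce. The calculation below shows what the stated rule can do.

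**Inputs from the documents**
- Arm sizes of 90 (MTX) and 45 (placebo): SAP 3.6.
- Infusion-reaction rate on pegloticase every 2 weeks in phase 3: 22/85 = 25.9%, which agrees with the 26% in Protocol 7.1.2. It is used here as a stand-in for placebo-arm ECG uptake: 0.26 x 45 = 11.7, taken as 12 subjects.

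**Assumed inputs**
- MTX-arm ECG uptake, varied from 5% to 26%.
- Numbers of subjects with an abnormal ECG.
- Share of subjects already abnormal at Screening, varied from 0% to 40%.

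**Step 1: the identity.** In one arm let N be the exposed subjects, e those with a post-Screening ECG, and a those with an abnormal one. The SAP percentage is

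a/e = (a/N) / (e/N).

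The MTX-to-placebo ratio of SAP percentages is therefore the ratio of per-subject abnormality rates divided by the ratio of ECG uptake. If MTX has the lower per-subject rate, the order reverses when the uptake ratio is smaller than the abnormality ratio.

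**Step 2: whole-number examples.** Placebo is 4 abnormal among 12 with an ECG, out of 45, throughout.

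| MTX arm (N = 90) | Per exposed subject, MTX vs placebo | SAP 11.7 rule, MTX vs placebo | Effect |
|---|---|---|---|
| 4 abnormal of 9 ECGs | 4/90 = 4.4% vs 4/45 = 8.9% | 4/9 = 44.4% vs 4/12 = 33.3% | order reverses |
| 3 abnormal of 9 ECGs | 3/90 = 3.3% vs 8.9% | 3/9 = 33.3% vs 33.3% | difference masked |
| 4 abnormal of 18 ECGs | 4.4% vs 8.9% | 4/18 = 22.2% vs 33.3% | direction kept |

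**Step 3: range over MTX uptake.** Assume per-subject abnormality rates of 4.5% (MTX) and 9% (placebo), with placebo uptake of 26%. The placebo figure under the rule is 9/26 = 34.6%. The MTX figure is 4.5% divided by uptake:

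| MTX uptake | 5% | 10% | 13% | 15% | 20% | 26% |
|---|---|---|---|---|---|---|
| MTX under SAP rule | 90.0% | 45.0% | 34.6% | 30.0% | 22.5% | 17.3% |

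The order reverses below 13% uptake (half the placebo uptake, matching the abnormality ratio of one half), the arms tie at 13%, and the direction is kept above it.

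**Step 4: abnormalities carried over from Screening.** Suppose a share s of subjects with an ECG was abnormal at Screening in both arms and stays so. Among the rest, assume new abnormalities in 10% (MTX) and 30% (placebo). The rule shows s + (1 - s) x 0.10 against s + (1 - s) x 0.30:

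| s | MTX | Placebo | Difference (points) | Ratio |
|---|---|---|---|---|
| 0% | 10% | 30% | 20 | 3.00 |
| 10% | 19% | 37% | 18 | 1.95 |
| 20% | 28% | 44% | 16 | 1.57 |
| 30% | 37% | 51% | 14 | 1.38 |
| 40% | 46% | 58% | 12 | 1.26 |

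An equal share in both arms dilutes a difference but cannot reverse it.

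**The case against.** The case for leaving the table alone has real substance.

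- **It is descriptive.** SAP 11.7 plans no test or confidence interval, and ECG findings are not among the safety endpoints in Protocol 9.6.1.5 or SAP 4.5. This stands.
- **The counts are visible.** SAP 6.1 and 13.2 call for the number of observations, the count before each percentage, and the arm size in the column heading. A careful reader can recompute the per-subject figure. This stands, although the row would still be called an incidence.
- **The events are handled elsewhere.** Infusion reactions, anaphylaxis and cardiovascular events are adjudicated. Protocol 9.6.7 compares the proportion of subjects with each adverse event of special interest by arm, with a difference, 95% confidence interval and Fisher's exact test. This stands and is the main reason the point is minor.
- **The denominator is declared and conventional.** SAP 13.2.5.2 defaults to subjects with an observation. The same section also says that denominators need careful thought and are usually the number exposed. Convention therefore does not settle the matter where being observed depends on treatment.
- **Dividing by all exposed subjects is not clean either.** It treats untested subjects as not abnormal and makes the percentage depend on how often ECGs were taken. This stands, and it argues for showing both denominators.

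A reader might also infer that the rule conceals a several-fold difference. With ECGs in 26% of placebo and 5% to 20% of MTX subjects, and half of them abnormal in each arm, the table shows 50% vs 50% while 13% vs 2.5% to 10% of all subjects are affected. The documents do not support that reading. With the abnormal fraction set equal, the whole gap is the assumed infusion-reaction difference, which is reported in its own right.

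**Conclusion.** The point holds as a minor one. SAP 11.7 applies the term incidence to the abnormal fraction within a subset formed after randomisation, and the numerator as written does not exclude abnormalities unchanged since Screening. The two arm percentages should not be read against each other as incidences. They can mask a difference and, for some uptake rates, reverse it.

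Three limits apply. First, masking or reversal is possible, not expected: only the 26% and the arm sizes come from the documents, and the 26% is a phase 3 infusion-reaction rate, not an ECG rate. Uptake here also depends on investigator discretion, on event ECGs being feasible, and on the sUA stopping rule that both arms follow. Second, the counting of Screening abnormalities is inferred from the absence of any restriction or shift table; the SAP does not state it outright. Third, a reader might conclude that cardiac safety would go unexamined or that the trial's safety comparison is compromised. The per-subject comparison of the events of special interest rules that out.

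**What to change.** Revise SAP 11.7 as follows:

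1. Show, by arm, the number of exposed safety-population subjects with at least one post-Screening ECG. For the Pegloticase + IMM Period, exposed means having received pegloticase, as SAP 11 already defines it.
2. Present a 3 x 3 shift from Screening category (normal, NCS, CS) to worst post-Screening category, and count as new only subjects whose category worsened.
3. Give that count over both the exposed safety population and the subjects with an ECG. Label it 'new abnormal ECG detected' in place of incidence, with a note that subjects without an ECG are unassessed.

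The cost is a short SAP edit and one reprogrammed table, using data already collected. The downside is that the exposed-subject percentage depends on how often ECGs were taken, which is why item 1 and the second denominator should stand beside it.

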### **11.8.      Physical Examination**

A complete physical examination will be performed at the Screening Visit, including assessment of HEENT, heart, lungs, abdomen, skin, extremities, neurological status and musculoskeletal including an assessment for the presence of tophi.

A targeted physical examination per investigator judgement will be conducted at Week -6, Day 1, and prior to administration of pegloticase at Weeks 4, 8, 12, 16, 20, 24, 36 and the non-infusion End of Pegloticase Infusions Visit (if applicable), Week 52/End of Study/Early Termination and 3 and 6 month Post Treatment Follow-up Visits; at a minimum this should include heart, lungs, and abdominal exam.

Clinically significant findings from the targeted physical examinations will be recorded as AEs.

Physical examination data will be listed. No summarizations of the physical examination data will be presented.

This document is confidential.

## **12. Changes from Analysis Planned in Protocol**

In those cases in which this SAP details changes from the analyses specified by the protocol, the analyses specified in this SAP will supersede those in the protocol. There are no changes from Amendment 3 of the protocol but details and clarifications are described in this SAP.

This document is confidential.

## 13. Programming Considerations

### 13.1. General Considerations

- All TLFs will be produced in landscape format.
- All TLFs will be produced using the Courier New font, size 8
- The data displays for all TLFs will have a minimum 1-inch margin on all 4 sides.
- Headers and footers for figures will be in Courier New font, size 8.
- Legends will be used for all figures with more than 1 variable, group, or item displayed.
- TLFs will be in black and white (no color)
- Specialized text styles, such as bolding, italics, borders, and shading will not be used in the TLFs, unless otherwise specified. On some occasions, superscripts 1, 2, or 3 may be used.
- Only standard keyboard characters will be used in the TLFs. Special characters, such as non-printable control characters, printer-specific, or font-specific characters, will not be used. Hexadecimal-derived characters will be used, where possible, if they are appropriate to help display math symbols (e.g.,  $\mu$ ). Certain subscripts and superscripts (e.g.,  $m^2$ ,  $C_{trough}$ ) will be employed on a case-by-case basis.
- Title case or mixed case will be used for all titles, footnotes, column headers, and programmer-supplied formats, as appropriate.
- 

### 13.2. Table, Listing, and Figure Format

#### 13.2.1. General

- Headers and footers for figures will be in Courier New font, size 8 which is the smallest acceptable point size for the Regulatory Authorities.
- Legends will be used for all figures with more than 1 variable, group, or item displayed.
- Tables, Figures and Listings (TLFs) will be in black and white (no color), unless otherwise specified
- Specialized text styles, such as bolding, italics, borders, shading, and superscripted and subscripted text, will not be used in the TLFs, unless otherwise specified. On some occasions, superscripts 1, 2, or 3 may be used (see below).
- Only standard keyboard characters will be used in the TLFs. Special characters, such as non-printable control characters, printer-specific, or font-specific characters, will not be used. Hexadecimal-derived characters will be used, where possible, if they are appropriate to help display math symbols (e.g.,  $\mu$ ). Certain subscripts and superscripts (e.g.,  $cm^2$ ,  $C_{max}$ ) will be employed on a case-by-case basis.
- Title case or mixed case will be used for all titles, footnotes, column headers, and programmer-supplied formats, as appropriate.

### 13.2.2. Headers

- All output should have the following header at the top left of each page:

Horizon Therapeutics Ireland DAC

Protocol HZNP-KRY-202

- All output should have Page n of N at the top or bottom right corner of each page. TLFs are internally paginated in relation to the total length (i.e., the page number should appear sequentially as page n of N, where N is the total number of pages in the table).
- The date output was generated should appear along with the program name as a footer on each page.

### 13.2.3. Display Titles

- Each Table, Figure, and Listing is identified by the designation and a numeral. (i.e., Table 14.1.1). ICH E3 numbering is strongly recommended, but sponsor preferences are obtained before final determination. A decimal system (x.y and x.y.z) will be used to identify TLFs with related contents. The title is centered. The analysis set are identified on the line immediately following the title. The title and table designation are single spaced. A solid line spanning the margins will separate the display titles from the column headers. There will be 1 blank line between the last title and the solid line.

Table x.y.z  
First Line of Title  
Second Line of Title if Needed  
(ITT Population)

### 13.2.4. Column Headers

- Column headings are displayed immediately below the solid line described above in initial upper-case characters.
- In the case of efficacy tables, the variable (or characteristic) column will be on the far left followed by the population columns. Within-treatment comparisons may have p-values presented in a row beneath the summary statistics for that treatment.
- For numeric variables, include “unit” in column or row heading when appropriate.
- Analysis set sizes will be presented for each treatment group in the column heading as (N=xx) (or in the row headings, if applicable). This is distinct from the ‘n’ used for the descriptive statistics representing the number of subjects in the analysis set.

### 13.2.5. Body of the Data Display

#### 13.2.5.1. General Conventions

Data in columns of a table or listing are formatted as follows:

- Alphanumeric values are left-justified;
- Whole numbers (e.g., counts) are right-justified; and
- Numbers containing fractional portions are decimal aligned.

#### 13.2.5.2. Table Conventions

- Units will be included where available
- If the categories of a parameter are ordered, then all categories between the maximum and minimum category are presented in the table, even if n=0 for all treatment groups in a given category that is between the minimum and maximum level for that parameter. For example, the frequency distribution for symptom severity will appear as:

Severity Rating	N
Severe	0
moderate	8
Mild	3

Where percentages are presented in these tables, zero percentages will not be presented and so counts of 0 will be presented as 0 and not as 0 (0%).

- If the categories are not ordered (e.g., Medical History, Reasons for Discontinuation from the Study, etc.), then only those categories for which there is at least 1 subject represented in 1 or more groups are included.
- An Unknown or Missing category are added to each parameter for which information is not available for 1 or more subjects.
- Unless otherwise specified, the estimated mean and median for a set of values are printed out to 1 more significant digit than the original values, and standard deviations are printed out to 2 more significant digits than the original values. The minimum and maximum should report the same significant digits as the original values. For example, for systolic blood pressure:

N	XX
Mean	XXX.X
SD	X.XX
Median	XXX.X

This document is confidential.

Minimum	XXX
Maximum	XXX

- Percentage values are printed to one decimal place, in parentheses with no spaces, one space after the count [e.g., 7 (12.8), 13 (5.4)]. Unless otherwise noted, for all percentages, the number of subjects in the analysis set for the treatment group who have an observation will be the denominator. Percentages after zero counts should not be displayed and percentages equating to 100% are presented as 100%, without decimal places.
- Tabular display of data for medical history, prior/concomitant medications, and all tabular displays of adverse event data are presented by the body system, treatment class, or SOC with the SOC (or treatment class) sorted alphabetically. Within the body system, drug class and SOC, medical history (by preferred term), drug term (by preferred name, and adverse events (by preferred term) are displayed alphabetically.
- The percentage of subjects is normally calculated as a proportion of the number of subjects assessed in the relevant treatment group (or overall) for the analysis set presented. However, careful consideration is required in many instances due to the complicated nature of selecting the denominator, usually the appropriate number of subjects exposed. Describe details of this in footnotes or programming notes.
- For categorical summaries (number and percentage of subjects) where a subject can be included in more than one category, describe in a footnote or programming note if the subject are included in the summary statistics for all relevant categories or just 1 category and the criteria for selecting the criteria.
- Where a category with a subheading (such as system organ class) has to be split over more than one page, output the subheading followed by "(cont)" at the top of each subsequent page. The overall summary statistics for the subheading should only be output on the first relevant page.

